6.3 Concomitant Medication

All medications and other treatments taken by subjects within 30 days before dosing and during the study will be recorded in the eCRF. Any medication/therapy that stops at or after the date and CONFIDENTIAL Page 15 of 33

time of start of treatment or those with missing stop dates are considered concomitant medication/therapy.

Concomitant medications will be coded using the March 1, 2018 version of the WHODrug. Subjects who take concomitant medications will be presented in a by-subject listing of verbatim and coded terms and summarized by drug class and preferred name, overall and by treatment group, for the safety population.

A by-subject listing of all concomitant medications will be presented. Additionally, a summary and by-subject listing of concomitant medications that were prescribed or modified at or after the time of discharge on study day will also be presented.

7 STUDY DRUG EXPOSURE

Gel application information is captured on eDiary. Subjects who miss the previous gel application entry (and only the previous one) will be allowed to enter the missed gel application when they login in prior to the next scheduled gel application diary. Since the actual gel application time for the missing gel application will not be captured at the next entry, the date/time for the missing gel application will be imputed with the previous scheduled gel application time. Details of each gel application will be displayed in data listings.

The study gel will be applied at the clinic on Days 1 and 2. The study gel for application on Day 1 will be dispensed by the site pharmacy, and for Days 2-8 will be dispensed to the subjects prior to discharge on Day 2. For subjects assigned to Period 2, study gel for application by subjects will be dispensed at the Day 8 and Day 15 Safety visits. Study gel tubes will be weighed, in grams, and the total weight for all tubes recorded prior to dispensing to subjects. Study gel will be collected on Day 8 (for Period 1 subjects) and Day 22 (for Period 2 subjects), weighed and the final weight recorded. Compliance will be determined from the final weight of the tubes compared to the expected decrease from the starting weight, based on the assigned dosing schedule (2.8 grams per dose × the number of doses).

The compliance will be measured by the ratio between actual weight decreased and the expected decrease from starting weight of a study gel tube. It will be summarized in a table by treatment group as well as displayed in a data listing for the safety population.

8 EFFICACY EVALUATION

8.1 Efficacy Endpoints

8.1.1 Primary Efficacy Endpoint

The primary efficacy endpoint for this study is the sum of PID between 0 (baseline) to 24 hours () for the study leg after the first study gel application while standing using a 0-100 point eVAS.

8.2 Handling of Dropouts or Missing data

CONFIDENTIAL Page 16 of 33

Missing VAS values up to 168 hours caused by early withdrawal from the study due to events which are not preferable to subjects such as an adverse event (AE) and/or lack of efficacy (LOE) will be imputed by last observation carried forward (LOCF).

If missing VAS values caused by withdrawal other than AE and/or LOE will be imputed for each treatment group separately under the missing at random (MAR) assumption with the multiple imputation (MI) technique. The imputation will be carried out in SAS version 9.4 or later, using the full conditional specification method (FCS) with a regression model approach (Carpenter and Kenward, 2013). By using the MI technique, 100 datasets will be generated. After calculating the SPID, an analysis of covariance (ANCOVA) model will be applied for the primary endpoint with gender and treatment as fixed effects and baseline pain as a covariate in each dataset. Multiple results will be combined using Rubin's rule (Little and Rubin, 1987), and will be done in SAS using PROC MIANALYZE. A significance test of the treatment difference at the two-sided 0.05 level and corresponding 95% confidence intervals will be calculated. However, the multiple imputation is used only for subjects that have a baseline.

If there exist missing VAS values to be imputed, any such values will be imputed before calculating the SPID. Intermediate missing VAS values due to an omission of recording pain intensity or subject's sleep will not be imputed, therefore, the observed values before and after the missing measurement will be directly connected in order to calculate the SPID. If subjects need to take the rescue medication, they will record their pain intensity in the eDiary before taking the rescue medication. If the rescue medication is taken within 6 hours of a nominal pain intensity assessment time point, the pain intensity score that was recorded before taking the rescue medication will be carried forward to the next pain intensity assessment time point.

8.2.1 Assessment Time Windows

Data are generally reported according to the nominal time of clinic visits and assessments as specified in the protocol. Refer Section 2.2.1 of this SAP (study design) for time windows for different assessments.

8.3 Analysis Method for the Primary Efficacy Endpoint

The primary efficacy endpoint for this study is the sum of PID between () for the study leg after the first study gel application while standing using a 0-100 point eVAS. The primary analysis of the primary endpoint will be based on the FAS.

CONFIDENTIAL Page 17 of 33

The durations between nominal time points will be calculated using the actual times of the pain score measurement. If the actual time is missing the nominal planned time will be used.

The primary endpoint will be analyzed using an ANCOVA model, which will include treatment and gender as fixed effects and baseline eVAS score as a covariate. The least square (LS) mean, standard error (SE) and associated 95% confidence interval (CI) for each treatment group will be estimated. In addition, the LS mean difference between each treatment group, SE, p-value and the associated 95% CI will also be computed. Descriptive summaries (including mean, SD, median, minimum, and maximum) will also be presented. Missing data imputation methodology is described in Section 8.2 in this SAP.

Distributional assumptions underlying the model used for analysis will be examined by obtaining a normal probability plot of the residuals and a plot of the residuals versus the fitted values (i.e., checking the normality assumption and constant variance assumption of the model respectively) to gain confidence that the model assumptions are reasonable. A nonparametric test may be conducted if the normality assumption is violated. An ANCOVA with unequal variances may be conducted if the constant variance assumption is violated.

To explore the impact of collecting e-diary data from different vendors, a sensitivity analysis by including both baseline eVAS score and the e-diary vendor in the model will be performed. Since majority of the eVAS data are collected by the second vendor, an analysis based on the second vendor's data only will be performed also.

8.4 Analysis Method for the Secondary Efficacy Endpoints

SPID Outcome	28
--------------	----

For non-study leg, after the first study gel application while standing using a 0-100 point eVAS, will be calculated, summarized, and analyzed similarly to primary endpoint.

The following secondary efficacy SPID outcomes are calculated and analyzed similarly to primary endpoint of sum of PID between for the study leg after the first study gel application while standing using a 0-100 point eVAS, adjusting for the respective time periods:

- SPID0-24 hours after the first study gel application at rest using a 0-100 point eVAS
- SPID between 0 (Baseline) to 12 hours (SPID0-12) after the first study gel application while standing using a 0-100 point eVAS
- SPID0-12 hours after the first study gel application at rest using a 0-100 point eVAS
- SPID between 0 (Baseline) to 48 hours (SPID0-48) after the first study gel application while standing using a 0-100 point eVAS
- SPID0-48 hours after the first study gel application at rest using a 0-100 point eVAS
- SPID between 0 (Baseline) to 72 hours (SPID0-72) after the first study gel application while standing using a 0-100 point eVAS
- SPID0-72 hours after the first study gel application at rest using a 0-100 point eVAS

CONFIDENTIAL Page 18 of 33

Change from Baseline in PID

The Mean change from Baseline in pain intensity difference (PID) while standing and rest at different time points, after the first study gel application using a 0-100 point eVAS, will be summarized descriptively.

Time-specific mean change from baseline in PID will be assessed using a mixed model repeated measures (MMRM) with PID as the dependent variable. Fixed effects of the model include treatment arm, time, the treatment arm by time interaction, baseline eVAS, and gender. Subject is a random effect. A completely general (unstructured) covariance matrix will be used. A first-order autoregressive covariance matrix will be used if the model with an unstructured covariance matrix does not converge. Pairwise comparisons at each time point will be determined from the MMRM, and model-based means (LS means) and standard errors will be plotted for visual comparison of the treatment group outcomes. Only scheduled measurements will be included in the MMRM.

Perceptible and Meaningful Pain Relief

Pain assessments of time to first perceptible pain relief and time to meaningful pain relief for both legs at rest and while standing will be recorded by subjects using their e-diary. At the time of first perceptible pain relief and at the time of meaningful pain relief, subjects will use their e-diary to record the time the events are experienced. Since these assessments will be captured in the e-diary, the electronic database will be the direct point of data capture and will serve as source for this variable.

Both time to perceptible and meaningful pain relief will be analyzed using Kaplan-Meier curves with the log-rank test. Subjects will be censored at the time of safety visit on Day 8 or at the time of dropout. Estimated median time to perceptible/meaningful pain relief as well as their 95% confidence intervals will be tabulated by treatment group along with the number and percent of subjects censored.

Rescue Medication Usage

CONFIDENTIAL Page 19 of 33

The proportion of subjects receiving rescue medication will be summarized descriptively by treatment group, using counts and percentages, along with 95% confidence intervals and CMH chi-square or Fisher exact *p*-values.

Time to first administration of rescue medication is the date/time of the earliest rescue medication use minus the date/time of administration of study drug. If the subject receives no rescue medication, then the value will be censored at 168 hours or at dropout.

Time to rescue medication will be analyzed using Kaplan-Meier curves with the log-rank test. Estimated median time to first use of rescue as well as its 95% confidence interval will be tabulated by treatment group along with the number and percent of subjects censored.

Total (mg) rescue medication used will be summarized descriptively. For each summary period
, the mean number of rescue medication per day and the percentage of rescue-free days will be calculated. For each period and overall, cumulative rescue medication use will be displayed. Any data recorded after 168 hours, will not be included in any summaries.

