The safety endpoint data will be summarized for the safety set. Adverse events will be coded using the latest version of the Medical Dictionary for Regulatory Activities (MedDRA). Adverse events and serious AEs (SAEs) will be summarized by treatment group for overall number of AEs, severity, and relationship to study gel. The incidence of AEs will be summarized by body system and treatment group. The incidence of treatment-emergent AEs (TEAEs) will also be summarized by system organ class and preferred term. Clinical laboratory results will be summarized by treatment group along with change from Baseline. Vital sign measurements will be summarized by group and time point along with change from Baseline. All AE, clinical laboratory, vital sign, physical examination, study gel application site reaction, study gel use and concomitant medication use will be presented in data listings.

[REDACTED]

Sample Size Calculation:

The parameters are conservatively estimated based on the DOMS study with [REDACTED] gel. The between-group difference in the mean [REDACTED] is 11.07 with a SD of 25.62. To have statistical power of 90%, 113 subjects per group are required. Taking into account information loss caused by missing data, it is estimated that 120 subjects need to be treated with each study gel.

TABLE OF CONTENTS

| | |
|---|------------|
| INVESTIGATOR’S STATEMENT | ii |
| SIGNATURE PAGE | iii |
| PROTOCOL SYNOPSIS | iv |
| LIST OF ABBREVIATIONS AND DEFINITION OF TERMS | xv |
| 1.0 INTRODUCTION AND RATIONALE FOR DOSE SELECTION | 1 |
| 1.1 BACKGROUND INFORMATION | 1 |
| 1.2 RATIONALE FOR STUDY AND DOSE SELECTION | 2 |
| 2.0 STUDY OBJECTIVES | 4 |
| 2.1 PRIMARY OBJECTIVE | 4 |
| 2.2 SECONDARY OBJECTIVES..... | 4 |
| 2.3 PRIMARY EFFICACY ENDPOINT | 4 |
| 2.4 SECONDARY EFFICACY ENDPOINTS | 4 |
| 2.5 SAFETY ENDPOINTS | 5 |
| 3.0 STUDY DESCRIPTION | 6 |
| 3.1 STUDY DESIGN | 6 |
| 4.0 SUBJECT ELIGIBILITY AND WITHDRAWAL CRITERIA | 14 |
| 4.1 INCLUSION CRITERIA | 14 |
| 4.1.1 Pre-exercise Inclusion Criteria..... | 14 |
| 4.1.2 Post-exercise Randomization Inclusion Criteria:..... | 15 |
| 4.2 EXCLUSION CRITERIA | 15 |
| 4.3 DISCONTINUATION AND WITHDRAWAL CRITERIA..... | 16 |
| 4.3.1 Discontinuation due to an Application Site Reaction | 17 |
| 5.0 PROCEDURES FOR EFFICACY AND SAFETY EVALUATIONS | 18 |
| 5.1 EFFICACY EVALUATIONS | 18 |
| 5.1.1 Pain Intensity | 18 |
| 5.1.1.1 Visual Analog Scale..... | 18 |
| 5.1.1.2 Categorical Pain Scale | 18 |

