2.2 Overall Study Design and Plan

2.2.1 Study Design

This is a phase II, randomized, double-blind, active comparator, parallel group study to evaluate the efficacy and safety of K-285 compared with menthol gel for the treatment of DOMS in the lower extremity. The study will consist of screening, an exercise visit (DOMS induction), in-patient and out-patient periods up to 3 weeks, and a follow-up telephone call.

During the Screening Visit, subjects will provide informed consent and complete screening assessments including medical history, identification of the dominant leg, physical and skin

CONFIDENTIAL Page 7 of 33

examinations, blood and urine tests, vital signs measurements, electrocardiogram (ECG), and other screening procedures. Subjects who are able to participate in the study (Period 1 and 2) and who meet the pre-exercise inclusion and exclusion criteria will be enrolled into the study and return to the clinic on Day -1.

[figure not shown]
Eligibility will be confirmed, and enrolled subjects will perform a standardized repetitive quadriceps muscle exercise to create DOMS to both legs (Day -1). The exercise regimen will consist of a warm-up, determination of maximum tolerated weight, and timed and untimed workout phases. Within 24 to 30 hours after the exercise session (Day 1), subjects will rate the pain of both legs using a categorical pain scale and record pain intensity of both legs at rest and while standing using a 0-100 point electronic visual analog scale (eVAS) (a capture program will linearly convert the pixel touched to an integer between 0 and 100) to determine eligibility for randomization. The specific post-exercise inclusion criterion will be masked to subjects.

If both legs meet post-exercise inclusion criteria, the study leg will be the dominant leg, based on hand dominance. Subjects not qualifying for randomization will be given appropriate standard of care.

A total of 240 subjects who meet post-exercise inclusion criteria will be randomly assigned in a 1:1 ratio to Treatment Arm A (K-285 gel) or Treatment Arm B (Menthol gel).

In period 1 study gels will be applied to randomized subjects on a on the study leg as follows:

 Treatment Arm A: Each subject will apply K-285 to the study leg CONFIDENTIAL Treatment Arm B: Each subject will apply menthol gel to the study leg

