2.2.5 Sample Size Determination

The parameters are conservatively estimated based on the DOMS study with gel. The between-group difference in the mean is 11.07 with a SD of 25.62. To have statistical power of 90%, Taking into account information loss caused by missing data, it is estimated that 120 subjects need to be treated with each study gel.

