2.2.6 Interim Analysis for Futility Assessment

. The interim analysis will assess the futility of the trial (conditional power <0.05) based on efficacy of K-285 to menthol gel using the FAS. That is, if the conditional power is less than 0.05 (i.e., < 5%), the study would have met the stopping rule/decision criteria to stop for futility. The conditional power will be calculated under the assumption that the effect size estimate at the interim analysis is true. See Section 11 of SAP for more details.

An independent team of biostatisticians and statistical programmers will perform the interim analysis within a folder that has restricted access to only the independent team members to maintain the blinding of the study.

Interim analysis was conducted using 120 randomized subject data on Feb 26, 2021. The study has met the stopping rule to stop for futility because the conditional power is less than 0.05. As a result, 126 subjects randomized before the interim analysis will be included in final analysis, rather than the planned 240 subjects.

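### The PID MMRM fits one baseline slope for all time points; a baseline-by-time term would guard the precision of the time-specific comparisons at almost no cost

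*SAP*

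**What the plan says.** SAP 8.4 (Change from Baseline in PID) models PID at the scheduled times with an unstructured covariance matrix, falling back to first-order autoregressive if that fit does not converge. On the mean structure it says: "Fixed effects of the model include treatment arm, time, the treatment arm by time interaction, baseline eVAS, and gender". Only treatment interacts with time. On the use of the model it says: "Pairwise comparisons at each time point will be determined from the MMRM". LS means and standard errors from the model are also plotted.

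The Protocol synopsis (Secondary Efficacy Analyses) gives the MMRM the main effects and covariate of the ANCOVA and mentions no interaction with baseline. Part of Protocol 11.5.2 is blacked out, but the SAP sentence on fixed effects is intact, and no visible text adds a baseline-by-time term.

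The eVAS runs from 0 to 100 (SAP 4.1.2). The exact PID time points are redacted. That they run from 1 to 168 h is an inference from the assessment windows in Protocol 3.1 and in footnote c of Protocol Table 2.

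The number available is reduced: "126 subjects randomized before the interim analysis will be included in final analysis, rather than the planned 240 subjects".

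**The concern.** A change score contains the baseline with a negative sign. Soon after the first application, pain is still close to its baseline level in each subject, and the change depends little on baseline. If soreness later falls toward zero in most subjects, the change becomes nearly the baseline with its sign reversed. A single coefficient has to compromise between these two situations.

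Where the common slope is off, baseline variation stays in the residual and a chance difference in baseline between arms is over- or under-corrected. At stake is the precision of the time-specific contrasts, which are what this model is meant to deliver. With about 63 subjects per arm there is little precision to spare.

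**Working it through.** **The plan's own figure.** The planning difference "is 11.07 with a SD of 25.62" (SAP 2.2.5), power is 90%, and SAP 8.2 sets the level: "A significance test of the treatment difference at the two-sided 0.05 level and corresponding 95% confidence intervals will be calculated".

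n = 2 × (1.95996 + 1.28155)² × (25.62/11.07)² = 2 × 10.507 × 5.356 = 112.6, so 113. This matches the synopsis: "To have statistical power of 90%, 113 subjects per group are required". These inputs belong to the planning endpoint, whose name is redacted, and not to PID at one time. They do not enter what follows. The documents give no precision figure for the MMRM.

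**Slope of PID on baseline.** By the formula in SAP 3, PID at time t is pain at t minus pain at time 0, so the slope is

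β_t = ρ_t × sd_t / sd_0 − 1,

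where ρ_t is the correlation with baseline and sd_t the between-subject SD at t. Just after baseline this is about ρ_t − 1, near 0. If scores collapse toward the floor, sd_t shrinks and β_t tends to −1. If pain falls by the same amount in everyone, ρ_t and sd_t do not change and neither does β_t. (The sentence before that formula defines PID with the opposite sign. That flips the sign of the slope and changes nothing else.)

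**Variance of the contrast at t.** With complete data, equal arms and treatment-by-time in the model, leaving gender aside:

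- own slope at each time: (4/N) × s_t²
- common slope b: (4/N) × [s_t² + (β_t − b)² × sd_0²]

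Here s_t is the residual SD. The ratio of standard errors is √[1 + (β_t − b)² sd_0² / s_t²]. Under an unstructured covariance S, b = 1′S⁻¹β / 1′S⁻¹1.

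**One case in numbers (assumed values).** N = 126, sd_0 = 15, pain resolving, β at 1 h = 0.03, b = −0.825, own-slope standard error 1.325. The added variance is (4/126) × (0.855 × 15)² = 5.22. The common-slope standard error is √(1.325² + 5.22) = 2.64, and the ratio is 2.64/1.325 = 1.99.

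**Standard error ratio, common slope versus own slope** (N = 126, 16 assumed time points; sd_0 = 15 in the resolving cases):

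| Assumed course | b | 1 h | 12 h | 24 h | 72 h | 168 h |
|---|---|---|---|---|---|---|
| Resolves; correlation with baseline fades faster | −0.83 | 1.99 | 1.28 | 1.10 | 1.00 | 1.31 |
| Resolves; correlation fades more slowly | −0.79 | 2.05 | 1.53 | 1.30 | 1.03 | 1.30 |
| Spread grows first, then resolves | −0.37 | 1.20 | 1.06 | 1.02 | 1.01 | 1.49 |
| No resolution, slope nearly constant | −0.09 | 1.00 | 1.00 | 1.00 | 1.00 | 1.01 |

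**A milder set.** Let the slope go from −0.11 at 1 h to −0.82 at 168 h, with b between −0.46 and −0.53, baseline SD 10 to 15 and residual SD 10 to 12. The corners of these ranges, which need not all occur together, give:

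- 1 h: √[1 + (10 × 0.35/12)²] = 1.04 to √[1 + (15 × 0.42/10)²] = 1.18
- 168 h: √[1 + (10 × 0.29/12)²] = 1.03 to √[1 + (15 × 0.36/10)²] = 1.14

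**Simulation.** 3,000 trials with N = 126, nine assumed time points and gender in the model gave these ratios at 1, 24 and 168 h, in the order of the table: 2.04, 1.11, 1.29; 2.09, 1.29, 1.26; 1.22, 1.02, 1.47; and 1.00 throughout. Mean error of the common-slope contrast was at most 0.11 points, against a Monte Carlo error of about 2.7/√3000 = 0.05. With a constant slope the extra term cost under 1% in standard error.

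**Imbalance and lost precision are one effect.** In the case above the SD of the chance baseline difference is √(4/126) × 15 = 2.67 points. Multiplied by the slope error 0.855 this is 2.28, and 2.28² = 5.2 is the added variance already counted.

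**The case against.** The strongest reply is that the premise is not in the documents. They describe no pain course, and no SD or correlation by time. They allow rescue medication from 168 h if it is needed (Protocol 5.1.2, SAP 4.1.4), so the plan itself allows for soreness at Day 8. A uniform fall in pain would leave the slope constant and the planned model fully efficient. A reader might infer that the slope must change, or that pain is near zero by Day 8. Neither is established. This part of the objection stands, and it makes the point conditional.

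Second, the size cannot be checked. The scenarios agree in direction when pain resolves, but range from no loss to a doubling at one time point. No single percentage, and no equivalent number of lost subjects, should be read as an estimate for this trial. This stands too.

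Third, a common slope is pre-specified, agrees with the protocol and is valid. The contrasts are secondary, and the trial has already met its futility rule. All true. That limits the importance of the point but is no reason to prefer the less flexible model.

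Fourth, the formulas assume complete data and a converged unstructured fit. With 126 subjects and many time points the autoregressive fallback is a real possibility. It forces equal variance over time, and the figures above do not carry over to it.

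**Conclusion.** The model fact is certain: one baseline coefficient serves all time points, while treatment is compared at each. That a common slope costs precision at the early and late times follows by algebra if pain falls toward the scale floor over the assessed period. That is plausible but not documented. The loss is least where the true slope is near the common one: around 48 to 120 h in most of these scenarios, and nil throughout if the slope is constant. At the extremes it ranges from a few percent to about double the standard error, depending wholly on assumed SDs, correlations and time points.

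Two stronger readings go too far. One is that the time-specific comparisons are biased or their type I error inflated. With complete randomized data, baseline differs between arms only by chance, and an unstructured covariance absorbs the leftover baseline variation, so the standard errors grow instead of being falsely small. The other is that the primary result is at risk. Each SPID ANCOVA estimates its own baseline slope, so the primary analysis and the SPID windows are untouched.

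This is a worthwhile, low-priority improvement to a secondary analysis.

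**What to change.** In SAP 8.4, add a baseline eVAS-by-time interaction to the fixed effects of the MMRM, for both the standing and the rest models, and keep it if the autoregressive fallback is used. The cost is one extra parameter for each additional time point, and under 1% in standard error in simulation when the slope is constant. If the SAP can no longer be changed, run the extended model as a supplementary analysis, labelled post hoc as SAP 1 provides, and report it beside the planned one.

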In general, assessments with continuous outcomes will be summarized using the descriptive statistics n, mean, standard deviation (SD), median, minimum and maximum. For assessments with categorical outcomes, frequency counts and percentage will be calculated. Detailed statistical methodology will be presented in a separate statistical analysis plan.

Study Populations:

Three analysis populations will be evaluated:

- The full analysis set (FAS) will include all randomized subjects who have a baseline pain score, and at least 1 study gel applied
- The per-protocol set (PPS) will include all randomized subjects who have a baseline pain score, at least 1 study gel applied, and no major protocol violations.
- The safety set will include all subjects who have at least 1 study gel applied.

Primary Efficacy Analysis:

The primary analysis population is the FAS. The primary analysis will be repeated using the PPS. [REDACTED]

[REDACTED]. If there exist missing VAS values to be imputed, any such values will be imputed before calculating the SPID. After calculating the SPID, an analysis of covariance (ANCOVA) model will be applied for the primary endpoint with gender and treatment as main effects and baseline pain as a covariate.

Secondary Efficacy Analyses:

A mixed effect model repeated-measures (MMRM) with the same main effects and covariate will be applied to the PID while standing and PID at rest to investigate treatment differences.

[REDACTED] The time to first dose of rescue medication, will be analyzed using the Kaplan-Meier method to estimate the survival distribution function.

Safety:

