11.5.2 Secondary Efficacy Parameters

A mixed effect model repeated-measures (MMRM) will be applied to the PID while standing and PID at rest to investigate treatment differences. [REDACTED]. [REDACTED]. The time to first dose of rescue medication, will be analyzed using the Kaplan-Meier method to estimate the survival distribution function.

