- The change from baseline will be calculated as post-baseline value minus baseline value. If either the baseline or post baseline value is missing, the change from baseline is set to missing as well.
- Pain intensity difference (PID) is to be calculated by subtracting the pain intensity at each time point from the pain intensity at time 0

$$PID_t = PI_t - PI_0$$

• The number of days in the study is computed as: [Date of study completion or withdrawal minus the date of first study drug administration] + 1.

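### The only fallback for the PID repeated-measures model is AR(1) with no robust standard errors; if it is used and residual variance changes over time, the per-time-point inference is wrong in an unknown direction

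*SAP*

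**What the plan says.** SAP 8.4 (Change from Baseline in PID) fits a mixed model for repeated measures to PID, standing and at rest. On the mean model: "Fixed effects of the model include treatment arm, time, the treatment arm by time interaction, baseline eVAS, and gender". Baseline therefore has one slope shared by all times. On the covariance: "Subject is a random effect. A completely general (unstructured) covariance matrix will be used". On failure to converge: "A first-order autoregressive covariance matrix will be used if the model with an unstructured covariance matrix does not converge". On what is read from the model: "Pairwise comparisons at each time point will be determined from the MMRM, and model-based means (LS means) and standard errors will be plotted".

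SAP 3 defines PID as a difference from the time 0 score ("calculated by subtracting the pain intensity at each time point from the pain intensity at time 0"). Protocol Table 2, footnote c, shows assessments running from 1 h to 168 h; the exact list of times is redacted.

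Protocol 11.5.2 says only "A mixed effect model repeated-measures (MMRM) will be applied to the PID while standing and PID at rest to investigate treatment differences", and the synopsis adds "with the same main effects and covariate will be applied to the PID while standing and PID at rest". Neither names a covariance structure in its readable text. Redacted text follows the model sentence in both places.

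**The concern.** A standard AR(1) matrix has two parameters: one variance and one correlation. The treatment comparison at every time point then gets nearly the same model-based standard error, however widely the scores really spread at that time. The SAP does not call its matrix homogeneous, but it names no heterogeneous form, no sandwich estimator and no degrees-of-freedom method.

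Constant residual variance over a week is a strong assumption here. The outcome is a change from time 0, the first assessments come within hours, baseline has one slope, and induced soreness may largely resolve by Day 8. Where the true residual spread is below the pooled value, the test is too cautious. Where it is above, the test rejects too often. At stake are the pairwise comparisons and the plotted standard errors at each time point in the standing and rest models.

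**Working it through.** The plan gives no figure for this model, so there is nothing of its own to reproduce. The question is how far the AR(1) standard error can be from the truth.

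**Inputs from the documents.** Mean model (SAP 8.4); PID definition (SAP 3), whose sign does not affect the variance; assessment span 1 h to 168 h (Protocol Table 2, footnote c); 126 subjects in the final analysis (SAP 2.2.6), taken as 63 per arm; two-sided 0.05 (SAP 8.2, stated there for the primary test).

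**Assumed.** Sixteen times: 1, 2, 4, 6, 8, 12, 18, 24, 36, 48, 60, 72, 96, 120, 144 and 168 h. Raw pain SD of 20 at baseline. Correlation of raw pain at a given lag: c = rel × [s + (1 − s) × exp(−lag/τ)], with (s, τ, rel) = A (0.2, 24, 0.95), B (0.4, 48, 0.90), C (0.5, 24, 0.80).

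**Step 1, residual SD.** With constant raw SD σ and baseline slope b, the residual variance of PID at time t is σ²[2(1 − c)(1 + b) + b²]. For set A the fitted b is about −0.50.
- At 168 h, c = 0.191, so the SD is 20 × √(2 × 0.809 × 0.50 + 0.25) = 20.6.
- At 1 h, c = 0.919, so the SD is 20 × √(2 × 0.081 × 0.50 + 0.25) = 11.5 (11.6 with the unrounded slope).

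**Step 2, AR(1) SD.** The limiting AR(1) fit to the residual covariance Σ minimises log|R(ρ)| + 16 × log(s²), where s² = tr(R⁻¹Σ)/16, with b estimated by generalised least squares. For set A, s = 17.5.

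**Step 3, ratio and type I error.** With complete data, the factor √(2/63) is common to the model SE and the true SE and cancels. So ratio = s / residual SD at t, and type I error = 2[1 − Φ(1.96 × ratio)]. For set A at 1 h: 17.5/11.6 = 1.51, and 2[1 − Φ(2.96)] = 0.3%.

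| Raw pain SD | Set | Residual SD at 1 / 24 / 168 h | AR(1) SD | Ratio 1 h (type I) | Ratio 168 h (type I) |
|---|---|---|---|---|---|
| Constant 20 | A | 11.6 / 17.7 / 20.6 | 17.5 | 1.51 (0.3%) | 0.85 (9.6%) |
| | B | 10.4 / 14.6 / 19.3 | 15.4 | 1.47 (0.4%) | 0.80 (11.8%) |
| | C | 13.2 / 16.7 / 18.6 | 16.6 | 1.26 (1.4%) | 0.89 (8.0%) |
| Halves every 24 h, floor 3 | A | 13.0 / 9.2 / 7.3 | 9.9 | 0.76 (13.8%) | 1.35 (0.8%) |
| | B | 12.9 / 7.3 / 7.3 | 9.3 | 0.72 (16.0%) | 1.26 (1.3%) |
| | C | 14.8 / 8.5 / 6.1 | 9.9 | 0.67 (18.9%) | 1.62 (0.1%) |
| Halves every 48 h, floor 3 | A | 12.8 / 12.5 / 7.9 | 11.2 | 0.87 (8.7%) | 1.42 (0.5%) |
| | B | 12.4 / 10.3 / 8.3 | 10.3 | 0.82 (10.6%) | 1.23 (1.6%) |
| | C | 14.5 / 11.8 / 7.0 | 11.2 | 0.77 (13.0%) | 1.60 (0.2%) |

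Constant raw SD and falling raw SD give opposite errors at both ends. An intermediate pattern, SD 20 to 48 h and then linear to 8 at 168 h, gives ratios of 1.09 to 1.27 at 1 h, 0.79 to 0.83 at 48 h (type I about 10% to 12%) and 1.19 to 1.48 at 168 h.

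**Step 4, control.** In simulated trials of 126 subjects (2,000 per scenario, with some skipped assessments and 10 dropouts) and constant residual SD, AR(1) with model-based standard errors gave ratios of 0.99 to 1.03 and type I error of 3.9% to 5.7%.

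**Step 5, remedy.** In the same simulations, over seven scenarios with changing SD, AR(1) with sandwich standard errors gave ratios of 0.95 to 1.01 and type I error of 4.2% to 6.4% (Monte Carlo SE about 0.5 points). A second simulation used 15 times, other pain models and complete data. It included large early rating noise with fast resolution. In that case model-based AR(1) gave 7.6% to 12.3% from 1 h to 24 h and at most 0.1% from 96 h. Sandwich errors gave 3.6% to 6.4%, and heterogeneous AR(1) 3.9% to 5.8%. A slow-recovery model there gave a ratio of 2.13 at 1 h, so the table is not an outer bound.

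**Step 6, the random effect.** A 16-time unstructured matrix already has 16 × 17/2 = 136 parameters. Adding a subject variance makes 137, with information rank 136, so the extra one cannot be estimated separately. Keeping it in the AR(1) fallback moved the constant-raw-SD ratios by at most 0.01.

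**The case against.** **The trigger is hypothetical.** The fallback matters only if the unstructured fit fails, and nothing in the documents says how likely that is. At most 4 of 18,000 simulated unstructured fits missed tolerance. Those fits had no random effect and used a different algorithm from SAS, so they do not settle it, but they give no sign that failure is to be expected. This stands.

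**The consequence is small.** The affected results are secondary per-time-point comparisons and plotted standard errors, in a trial that SAP 2.2.6 says has already met its futility rule. This stands too.

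**A reader might infer a direction:** too cautious soon after baseline, too liberal later, with lost early power. PID is zero at time 0, which makes that look natural. The documents do not support it. They give no variance by time, and plausible falling patterns reverse it at both ends. No power-loss figure can be given for the same reason.

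**A reader might see an inconsistency with SAP 8.3**, which says "An ANCOVA with unequal variances may be conducted if the constant variance assumption is violated". That is a weak comparison. It concerns a single SPID value per subject, checked against fitted values, and it is optional. It says nothing about variance across times.

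**A reader might think that the random-effect wording makes the fallback likely.** It may be only loose wording for the repeated-measures unit, and no evidence here shows that it causes failure.

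**Hidden text.** The redacted protocol spans might name a structure. The SAP sentence is readable and complete, so the point rests on that.

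**Conclusion.** The point holds as a conditional weakness in a secondary analysis. If the unstructured model does not converge, if AR(1) is fitted in its standard one-variance form with model-based standard errors, and if residual variance changes over the week, then inference at individual time points is wrong. The tabulated ranges show the possible size. The schedule and all variances behind them are assumed, and the error can go either way at any time point. If residual variance is constant, AR(1) is sound.

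The primary ANCOVA, the SPID analyses and the Kaplan-Meier analyses do not use this model and are unaffected. Not knowing the direction is itself a reason for a fallback that is valid either way. This is worth a one-sentence change and does not threaten the trial's main conclusion.

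**What to change.** Replace the fallback sentence in SAP 8.4 with, for example: *Should the unstructured fit fail to converge, the model will be refitted with an AR(1) matrix and empirical (sandwich) standard errors, using between-subject degrees of freedom. The structure used will be reported for the standing and the rest model.*

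A heterogeneous-variance structure such as ARH(1) or ANTE(1) may be tried first, also with sandwich standard errors, provided AR(1) with sandwich standard errors remains the last step. At 16 times ANTE(1) needs 31 covariance parameters against 2 for AR(1), so it should not be the only alternative.

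As a wording change only, say that subject is the repeated-measures unit and that no separate random effect is fitted with the unstructured matrix.

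The cost is one line of code and no new data. Sandwich standard errors are slightly more variable at 126 subjects. They correct the standard error only. They would not remove bias if dropout depends on earlier scores and the working covariance is wrong; the simulations used complete data or dropout at random times and did not test this.
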